6.3.1 Decimal Places

Decimal places for derived data described in Section 6.1.4 will be determined by the scale of measurement unless otherwise stated. No decimal places will be displayed if the smallest calculated value is ≥ 100 ; 1 decimal place will be displayed when the smallest value is within the interval (10, 100), with 10 being inclusive; 2 decimal places will be displayed when the smallest value is within (1, 10), with 1 being inclusive; and so on for even smaller scales of measurement.

Derived data known in advance of the results will be given as an integer. For example day, month, year, number of days and total scores (for rating scales) will be presented with zero decimal places.

Means, medians and percentiles will be displayed to one more decimal place than the data, dispersion statistics (e.g. standard deviation) will have two more decimal places, and the minimum and maximum will be displayed to the same number of decimal places as reported in the raw data. Percentages will be displayed with one decimal place.

P- Values will be quoted to 3 decimal places.

6.4 Subject Disposition

Subject disposition will be summarized and listed as follows:

- The number of subjects, who entered the study, were randomized, and who are in each analysis set will be summarized by treatment group and overall for the Enrolled Set.
- The number of subjects who failed screening and the reasons for failure will be tabulated for the Enrolled Set.
- Eligibility Criteria violations will be presented for Enrolled Set.

QMD Ref: Worldwide-TMP-ST-005-7.0 Effective: 12Aug2019	Governing QMD: Worldwide-SOP-ST-001
Confidentiality Statement	
This document is the property of Worldwide Clinical Trials Inc. and may not be duplicated, copied, altered or removed from company without prior approval from Worldwide Quality Assurance or in compliance with Worldwide Standard Operating Procedures.	

Worldwide Clinical Trials Controlled Quality Management Document		
 WORLDWIDE CLINICAL TRIALS	Sponsor:	Synaptogenix, Inc.
	Protocol Number:	NTRP-101-204
STATISTICAL ANALYSIS PLAN. PHASE 2-3-4		

- The number of early withdrawals and the reasons for withdrawals will be tabulated by treatment group and overall for the Enrolled Set.
- Number of subjects in the SAS by site
- Number of subjects by visit for the SAS

6.5 Protocol Deviations

Protocol deviations will be summarized by treatment group and overall.

Also a listing of protocol deviations will be provided.

6.6 Baseline Comparability

The comparability of treatment groups with respect to subject demographics and baseline characteristics will be assessed in a descriptive manner, but no formal statistical testing will be performed.

Standard continuous or categorical variable summaries will be presented by treatment group determined by the treatment actually received for the following variables based on the SAS and on the FAS.

- Demographic data
- Disease history
- Medical history
- Neuroimaging
- Neuropsychological assessments at screening:
 - Severe Impairment Battery (SIB)
 - Mini Mental State Examination, 2nd edition (MMSE-2)
 - Alzheimer’s Disease Cooperative Study – Activities of Daily Living - Severe Impairment Version (ADCL-ADL-Sev)
 - Neuropsychiatric Inventory (NPI) metrics
 - Columbia Suicide Severity Rating Scale (C-SSRS)
- Physical examination by body system at screening
- Rosen-modified Hachinski Scale

QMD Ref: Worldwide-TMP-ST-005-7.0 Effective: 12Aug2019	Governing QMD: Worldwide-SOP-ST-001
Confidentiality Statement	
This document is the property of Worldwide Clinical Trials Inc. and may not be duplicated, copied, altered or removed from company without prior approval from Worldwide Quality Assurance or in compliance with Worldwide Standard Operating Procedures.	

Worldwide Clinical Trials Controlled Quality Management Document		
 WORLDWIDE CLINICAL TRIALS	Sponsor:	Synaptogenix, Inc.
	Protocol Number:	NTRP-101-204
STATISTICAL ANALYSIS PLAN. PHASE 2-3-4		

All Baseline data will also be listed.

6.7 Medical History

Separate tabulations of previous and ongoing conditions at screening will be presented by randomized treatment group and overall for the SAS and the FAS. Medical History will be considered as previous if the start date and end date is less than date of first dose. Medical History will be considered as ongoing if the start date is greater than or equal to date of first dose or if end date is greater than or equal to date of first dose. Conditions will be coded using Medical Dictionary of Regulated Activities (MedDRA, version 23.0 or later) primary system organ class (SOC) and preferred term (PT).

All Medical History data will also be listed.

6.8 Prior and Concomitant Medications

Separate tabulations will be produced for prior and concomitant medications presented by randomized treatment group and overall for the SAS and the FAS. Prior medications are defined as all medications starting before the date of first dose of study drug. Concomitant medications are defined as medications taken on or after the date of first dose of study drug. Concomitant medications will be coded using WHO Drug dictionary version March 2020 (or later) and summarized using Anatomic Therapeutic Chemical (ATC) Level 2.

6.9 Exposure to Study Drug

Data on exposure will be presented by randomized treatment group, overall, and by visit/whole study for the Safety Analysis Set. Following parameters will be presented in a table:

- For each visit:
 - Subjects who had an infusion
 - Subjects that received full infusion
 - Subjects that had at least 1 interruption
 - Subjects that received partial infusion
- For whole study

QMD Ref: Worldwide-TMP-ST-005-7.0 Effective: 12Aug2019	Governing QMD: Worldwide-SOP-ST-001
Confidentiality Statement	
This document is the property of Worldwide Clinical Trials Inc. and may not be duplicated, copied, altered or removed from company without prior approval from Worldwide Quality Assurance or in compliance with Worldwide Standard Operating Procedures.	

Worldwide Clinical Trials Controlled Quality Management Document		
 WORLDWIDE CLINICAL TRIALS	Sponsor:	Synaptogenix, Inc.
	Protocol Number:	NTRP-101-204
STATISTICAL ANALYSIS PLAN. PHASE 2-3-4		

- Subjects that received all full infusions
- Subjects that had at least 1 interruption
- Subjects that received at least 1 partial infusion
- Subjects who received 1 unfusion, ≥ 2 infusion and so on.
- Total volume of bryostatin infused
- Subjects who had $\geq 80\%$ of planned dose

All data on exposure will also be listed.

6.10 Treatment Compliance

Number and percentage of subjects receiving at least 80% of planned dose will be presented.

6.11 Efficacy Analyses

All statistical tests will be performed using a two-tailed 5% overall significance level, unless otherwise stated. All comparisons between treatments will be reported with 95% confidence intervals for the difference.

6.11.1 Primary Endpoint

The primary efficacy endpoint is the change from the pre-treatment baseline in the SIB total score at Week 28, after two 12-week courses of treatment.

6.11.2 Primary Efficacy Analysis

The primary efficacy analysis will be performed using linear mixed model with repeated measures (MMRM) with SIB measured at baseline as covariate, visit treated as a continuous as well as categorical variable, treatment and treatment by visit interaction. Categorical visit will be used to identify the ordering of measurements within a subject, while continuous visit will be used as covariate alone as well as in interaction with treatment.

Week of planned visits will be used as values of categorical variable of visit. Actual study day of visits (calculated in weeks) will be used as values of continuous variable of visit. The dependent

QMD Ref: Worldwide-TMP-ST-005-7.0 Effective: 12Aug2019	Governing QMD: Worldwide-SOP-ST-001
Confidentiality Statement	
This document is the property of Worldwide Clinical Trials Inc. and may not be duplicated, copied, altered or removed from company without prior approval from Worldwide Quality Assurance or in compliance with Worldwide Standard Operating Procedures.	

Worldwide Clinical Trials Controlled Quality Management Document		
 WORLDWIDE CLINICAL TRIALS	Sponsor:	Synaptogenix, Inc.
	Protocol Number:	NTRP-101-204
STATISTICAL ANALYSIS PLAN. PHASE 2-3-4		

variable will be the change from baseline in SIB total score at weeks 5, 9, 13, 15, 20, 24, 28, and 30.

Correlation between repeated observations within a subject will be accounted for by specifying an unstructured correlation. If this model does not converge then the following covariance matrices will be used in this particular order until the model converges: Toeplitz, compound symmetry, and first-order autoregressive.

Analysis will be performed using PROC MIXED in SAS, and the resulting F-tests will be based on using Kenward-Roger’s adjusted degrees of freedom.

The treatment groups will be compared at all timepoints using a two-sided test at a 5% significance level, with the primary comparison being the difference in group means of SIB from baseline at Week 28.

The sample SAS code below implements the model detailed above with an unstructured covariance matrix (TYPE = UN in the REPEATED statement). The code assumes that AVISITN has 8 values (one for each post-baseline visit), and TRT01PN representing treatment is coded as 1 = bryostatin, 2 = placebo.

```
proc mixed data = ;
  class subjid trt01pn avisitn;
  model sibdiff = sibbase trt01pn avisitd trt01pn* avisitd /
ddfm = kr outpred = pred;
  repeated avisitn / type = un subject = subjid;
  estimate "Bryostatin vs Placebo at week 28" trt01pn 1 -1
trt01pn* avisitd 28 -28 / cl;
run;
```

Variables names:

- subjid – unique number of subject,
- avisitn – visit as categorical variable,
- avisitd – visit as continuous variable,
- sibase – SIB at baseline,

QMD Ref: Worldwide-TMP-ST-005-7.0 Effective: 12Aug2019	Governing QMD: Worldwide-SOP-ST-001
Confidentiality Statement	
This document is the property of Worldwide Clinical Trials Inc. and may not be duplicated, copied, altered or removed from company without prior approval from Worldwide Quality Assurance or in compliance with Worldwide Standard Operating Procedures.	

Worldwide Clinical Trials Controlled Quality Management Document		
 WORLDWIDE CLINICAL TRIALS	Sponsor:	Synaptogenix, Inc.
	Protocol Number:	NTRP-101-204
STATISTICAL ANALYSIS PLAN. PHASE 2-3-4		

sibdiff – SIB difference from baseline,

trt01pn – treatment group.

As a sensitivity analysis the same model but using only categorical visit will be used. The following SAS code implements this model (the variable designations are the same):

```
proc mixed data = ;
  class subjid trt01pn avisitn;
  model sibdiff = sibbase trt01pn avisitn trt01pn* avisitn /
ddfm = kr outpred = pred;
  repeated avisitn / type = un subject = subjid;
  estimate "Bryostatin vs Placebo at week 28" trt01pn 1 -1
trt01pn* avisitn 0 0 0 0 0 0 1 0 0 0 0 0 0 0 -1 0 / cl;
run;
```

Patients that have missing SIB outcome data will be included in the primary analysis if they have complete SIB data for at least one follow-up timepoint (i.e., available case analysis). Although there is no universally acceptable, adequate method for analyzing longitudinal clinical trial data under ITT with missing primary endpoints, the available case analysis using a generalized linear mixed model approach such as MMRM will produce unbiased estimates of the treatment effect if the missingness is ignorable (i.e. missing completely at random or missing at random)^{2,3}.

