4 INVESTIGATIONAL PLAN

4.0 Overview of Study Design

This is a randomized double-blind placebo-controlled exploratory study assessing bryostatin for the treatment of moderately severe Alzheimer's disease in subjects not receiving memantine treatment. The first treatment period of the study is 15 weeks in duration, including safety and efficacy evaluation 30 days after the last treatment. Eligible subjects will be stratified based on SIB total scores at baseline and will be randomized 1:1 to treatment with 20 μ g bryostatin or placebo for two 12-week courses of treatment. The balance by treatment arms of baseline SIB total scores will be monitored in real time. Study drug is administered IV by continuous infusion. The first two doses of study drug will be a loading dose 20% higher (i.e., 24 μ g) than the assigned dose and will be administered one week apart. Thereafter, the assigned dose of 20 μ g will commence with the third dose and be administered every other week for 5 doses. The second treatment period, beginning at Week 15, will be identical to the first. Subjects are scheduled to receive seven doses over 12 weeks during the first treatment period and seven doses over 12 weeks in the second period according to the original blinded, randomized treatment assignment. Safety and efficacy assessments will be

CONFIDENTIAL

done as indicated on the Schedule of Activities (Table 1). The primary endpoint is the total SIB score assessment obtained at Week 28, after completion of two courses of treatment.

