9.5.1 SIB total score from baseline at the Week 42 follow-up visit

Treatment differences in SIB total score from baseline at Week 42, for subjects who completed that visit, will be estimated using an ANCOVA model that will adjust for baseline SIB total scores, baseline MMSE-2 scores, age, and gender.

9.5.2 SIB total score from baseline at Week 13

An ANCOVA model as described in Section 9.5.1 will be created to estimate the difference in SIB total scores at Week 13. Again, as with the SIB difference at Week 42. The ANCOVA model will adjust for baseline SIB, baseline MMSE-2 scores, age, and gender.

9.5.3 SIB total scores from baseline at Weeks 9, 20, 24 and 30

The linear regression models using the method of GEE as described in Sections 9.4 and 9.5.2 will be used to estimate the treatment difference in mean SIB total scores from the original baseline (i.e. at screening) at Weeks 9, 20, 24 and 30. As described in Section 9.4, weighted GEE will be used to account for data that are missing at random.

9.5.4 SIB total scores from baseline at Weeks 5, 9, 15, 20, and 24 for subjects with baseline MMSE-2 scores of 10-14 and 15-18

The estimation of the treatment differences at Weeks 9, 20, 24 and 30 for patients within each MMSE-2 group will be based on GEE linear regression model utilizing SIB total scores from baseline at these five time points. As described in Section 9.4, weighted GEE will be used to account for data that are missing at random.

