4 SAMPLE SIZE

The power analysis for the current study is based on a minimum clinically significant difference in mean total SIB scores from baseline of 4 points between the placebo and bryostatin arms at Week 28. Since the analysis of this primary outcome is based on a linear regression model that utilizes the total SIB scores at Weeks 0, 5, 9, 13, 15, 20, 24, and 28, a difference of approximately 0.15 points per week in the slope of total SIB scores between the placebo and bryostatin arms yields the clinically meaningful difference of 4 points at Week 28. General estimating equations (GEE) power analysis is based on the following equation:

QMD Ref: Worldwide-TMP-ST-005-7.0 Effective: 12Aug2019	Governing QMD: Worldwide-SOP-ST-001
Confidentiality Statement	
This document is the property of Worldwide Clinical Trials Inc. and may not be duplicated, copied, altered or removed from company without prior approval from Worldwide Quality Assurance or in compliance with Worldwide Standard Operating Procedures.	

Worldwide Clinical Trials Controlled Quality Management Document		
 WORLDWIDE CLINICAL TRIALS	Sponsor:	Synaptogenix, Inc.
	Protocol Number:	NTRP-101-204
STATISTICAL ANALYSIS PLAN. PHASE 2-3-4		

$$m = \frac{2(z_{\alpha/2} + z_{\beta})^2 \sigma^2 (1 - \rho)}{ns_x^2 d^2} \quad \text{Eq 1}$$

In equation 1, m is the number of patients per group, $z_{\alpha/2}$ is the type I error rate, z_{β} is the type II error rate, σ is the standard deviations of the error (residual) terms, ρ is the within person correlation of total SIB scores over time within a person, n is the time points where the total SIB score is obtained, s_x^2 is the variance of the X predictor variable (i.e. time in the current scenario), and d is the difference in slopes over time in total SIB measures from baseline between the placebo and bryostatin arms.

Based on the data from the NTRP101-202 study among patients without memantine, we obtained an estimate for $\sigma = 5.3$. In addition, the NTRP101-204 study will have SIB total scores measured at $n = 8$ timepoints, giving a value of $s_x^2 = 127$. Assuming a total of 100 patients (50 patients per arm), a two-sided type I error rate of 0.05 (i.e. $z_{\alpha/2} = 1.96$), and moderate within person correlation of outcome measures (i.e. $\rho = 0.5$), we will have > 99% power to see a difference in slopes over time of $d = 0.15$ points per week. In addition, we will have > 99% power to see this difference if we experience a 20% drop out.

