5 RANDOMIZATION

Once all eligibility criteria for the study have been met, and the site has received approval by the Medical Monitor (MM) and Clinical Assessment Technologies (CAT) group, via the Electronic Data Capture (EDC) system, the subject can be randomized via Interactive Response Technology (IRT) system. Randomization will be stratified by SIB total score at baseline and baseline SIB scores will be balanced at baseline between the treatment groups. Mean values of baseline SIB total scores by group will be monitored in real time during the enrollment process. A randomization number will be assigned, and drug for that randomization number will be shipped to the site for

QMD Ref: Worldwide-TMP-ST-005-7.0 Effective: 12Aug2019	Governing QMD: Worldwide-SOP-ST-001
Confidentiality Statement	
This document is the property of Worldwide Clinical Trials Inc. and may not be duplicated, copied, altered or removed from company without prior approval from Worldwide Quality Assurance or in compliance with Worldwide Standard Operating Procedures.	

Worldwide Clinical Trials Controlled Quality Management Document		
 WORLDWIDE CLINICAL TRIALS	Sponsor:	Synaptogenix, Inc.
	Protocol Number:	NTRP-101-204
STATISTICAL ANALYSIS PLAN. PHASE 2-3-4		

twelve weeks of treatment. Randomization and scheduling of the first study drug infusion should be timed to allow for receipt of study drug prior to the scheduled study treatment. The drug kits will be shipped to the individual who will be responsible for kit storage and drug preparation and may not be handled by any other study staff member. The study drug kit will not identify the vial containing study drug as either placebo or bryostatin. After completion of Week 13, a second study drug kit will be provided for treatment period two. The IRT system will be used to register subjects for treatment and trigger study drug shipments.

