6.11.4.1 SIB total score at the Week 42 follow-up visit

This endpoint will be analyzed using an Analysis of Covariance (ANCOVA) model with SIB score at Week 42 as dependent variable; treatment group as factor, and baseline SIB total score, baseline MMSE-2 score, age and gender as covariates.

6.11.4.2 The change from baseline in SIB total score at Week 13

This endpoint will be analyzed using the same ANCOVA model as described in Section 6.11.6.1.

6.11.4.3 SIB total scores from baseline at Weeks 9, 20, 24 and 30

This endpoint will be analyzed using the same MMRM model as described in Section 6.11.2 with corrections for obtaining results on corresponding visits.

6.11.4.4 SIB total scores from baseline at Weeks 9, 20, 24 and 30 for subjects with baseline MMSE-2 scores of 10-14 and 15-18

This endpoint will be analyzed using the same MMRM model as described in Section 6.11.2 with additional fixed effect for grouped baseline MMSE-2 scores (10-14 and 15-18) and corrections for obtaining results on corresponding visits.

QMD Ref: Worldwide-TMP-ST-005-7.0 Effective: 12Aug2019	Governing QMD: Worldwide-SOP-ST-001
Confidentiality Statement	
This document is the property of Worldwide Clinical Trials Inc. and may not be duplicated, copied, altered or removed from company without prior approval from Worldwide Quality Assurance or in compliance with Worldwide Standard Operating Procedures.	

Worldwide Clinical Trials Controlled Quality Management Document		
 WORLDWIDE CLINICAL TRIALS	Sponsor:	Synaptogenix, Inc.
	Protocol Number:	NTRP-101-204
STATISTICAL ANALYSIS PLAN. PHASE 2-3-4		

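### The primary MMRM adjusts only for baseline SIB, while the Week 13 and Week 42 SIB ANCOVAs also adjust for MMSE-2, age and gender; carrying the fuller set into the primary model is a modest, low-cost improvement

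*SAP*

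**What the plan says.** **Primary model.** SAP 6.11.2 describes an MMRM for change in SIB "with SIB measured at baseline as covariate", plus treatment, visit and treatment by visit. The code agrees: "model sibdiff = sibbase trt01pn avisitd trt01pn* avisitd". The second code block, for the sensitivity analysis with categorical visit, also has baseline SIB as its only baseline covariate. Protocol 9.4 names no covariates for the primary regression.

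**Week 42 and Week 13.** SAP 6.11.4.1 specifies an ANCOVA for Week 42 with "treatment group as factor, and baseline SIB total score, baseline MMSE-2 score, age and gender as covariates". SAP 6.11.4.2 uses the same ANCOVA for Week 13. It points to a section 6.11.6.1 that does not exist, but Protocol 9.5.2 settles the meaning: "The ANCOVA model will adjust for baseline SIB, baseline MMSE-2 scores, age, and gender". Protocol 9.5.1 lists the same four covariates for Week 42.

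**Design.** SAP section 5 states: "Randomization will be stratified by SIB total score at baseline". It names no other stratification factor. Allocation is 1:1 (Protocol 4.0).

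**Explanation.** SAP section 9 lists three departures from the protocol analysis. None concerns covariates.

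**The concern.** The three extra covariates are available before dosing: MMSE-2 and demographics are screening items in the protocol's Schedule of Activities. The plan uses them for two secondary SIB analyses, one of them at Week 42, a visit that protocol version 6.0 removed and for which only some subjects will have data. The primary comparison does not use them.

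Two things are at stake, both small:

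- **Precision.** If MMSE-2, age or gender predict SIB change beyond baseline SIB, prespecified adjustment would narrow the Week 28 interval without biasing a randomized comparison. Studies 202 and 203 stratified on MMSE-2 (Protocol 2.1.1.1 and 2.1.2.1). This trial does not, so in the primary analysis MMSE-2 is neither a design factor nor a covariate.
- **Consistency.** SAP 6.11.2 compares the groups at every visit, including Week 13, and 6.11.4.2 estimates Week 13 again with a different covariate set. The two models differ in form anyway. The unexplained difference in covariates adds one more reason for the two results to disagree.

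**Working it through.** **1. Inputs.** From SAP section 4: 50 per arm, 40 per arm after 20% dropout, SD 5.3, within-person correlation 0.5, 8 time points, variance of time 127, slope difference 0.15 per week, and "a two-sided type I error rate of 0.05". From SAP 6.11.2: post-baseline visits at Weeks 5, 9, 13, 15, 20, 24, 28 and 30. Neither document gives the share R² of residual variance that MMSE-2, age and gender explain once baseline SIB is known. I assume 0, 2, 5 and 10%.

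**2. The plan's own figure.** Equation 1 solved for power is Φ(√[m·n·s²ₓ·d² / (2σ²(1-ρ))] - 1.96).

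- 50 per arm: 50 × 8 × 127 × 0.0225 / 28.09 = 40.69. The root is 6.379, and Φ(4.419) = 99.9995%.
- 40 per arm: 32.55. The root is 5.705, and Φ(3.745) = 99.99%.

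The stated power above 99% reproduces. The visit weeks listed in SAP section 4 give a variance of 79.4, not 127. Power is then 99.9% and 99.5%, so the statement still holds.

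Equation 1 concerns the slope only. Covariates that are constant over time do not affect a slope difference, so this power is the same with or without them.

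**3. The Week 28 contrast in the primary model.** The estimate is an intercept difference plus 28 times a slope difference. I assume compound symmetry, complete data and conditioning on baseline SIB.

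- Between-subject variance: 28.09 × (0.5 - 0.25) = 7.02
- Within-subject variance: 28.09 × 0.5 = 14.05
- Single-visit residual variance: 7.02 + 14.05 = 21.07

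The eight visits have mean 18 and sum of squares 568. Per arm and per subject, the contrast variance has two parts:

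- Mean-level part: 7.02 + 14.05/8 = 8.78
- Slope part: 14.05 × (28 - 18)²/568 = 2.47
- Total: 11.25

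The SE at 50 per arm is √(11.25 × 2/50) = 0.671.

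**4. Adding the covariates.** They remove R² × 21.07 from the mean-level part and leave the slope part alone. The cost is an expected inflation of the mean-level part by (f - 1)/(f - 4), where f is the residual degrees of freedom before they enter. With 100 patients f = 97 and the factor is 96/93 = 1.032. With 80 patients f = 77 and the factor is 76/73 = 1.041.

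| Assumed R² | Mean-level part after removal | × 1.032 | Plus slope part | SE ratio, N=100 |
|---|---|---|---|---|
| 0% | 8.78 | 9.06 | 11.53 | 1.013 |
| 2% | 8.36 | 8.63 | 11.10 | 0.993 |
| 5% | 7.72 | 7.97 | 10.45 | 0.964 |
| 10% | 6.67 | 6.89 | 9.36 | 0.912 |

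The SE therefore changes by about +1%, -0.7%, -4% and -9%.

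Break-even is at R² = 8.78 × (3/96)/21.07 = 1.3% with 100 patients, and 8.78 × (3/76)/21.07 = 1.6% with 80.

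**5. The categorical-visit sensitivity model.** In a single-visit approximation the SE ratio is √[(1 - R²) × 1.032]. At 2, 5 and 10% this is 1.006, 0.990 and 0.964. Break-even is about 3% with 100 patients and 4% with 80, so the gain here is smaller.

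**The case against.** The strongest reply is that this is a preference. The model is prespecified, and it contains the only stratification factor. No figure in either document shows that MMSE-2, age or gender predict SIB change once baseline SIB is known, and MMSE-2 probably overlaps with SIB. All of that stands.

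Some stronger readings are tempting, and the documents do not support them.

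- **That precision is being given up for free.** No R² is given, and three uninformative covariates would cost about 1% in the primary SE.
- **That chance imbalance in severity goes uncorrected into the primary estimate.** Baseline SIB measures severity on the outcome's own scale. It is stratified, monitored by arm during enrollment and adjusted for. Entry limits (SIB 60-93, MMSE-2 10-18, age 55-85) narrow the ranges further. Only imbalance that remains after SIB adjustment is left.
- **That the primary and the secondary results as a whole rest on different covariate sets.** Only Weeks 13 and 42 do. The analyses at Weeks 9, 20, 24 and 30 and the slopes reuse the 6.11.2 model; the MMSE-2 subgroup analysis adds only a grouped MMSE-2 term.

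One counter-argument goes too far: that at 2% explained variance the change would be a net loss. This follows from the single-visit approximation in step 5. It does not hold for the linear-time primary contrast, where break-even is 1.3% to 1.6%.

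The objection that the edit is not confined to one line is correct. The 6.11.2 model is reused in 6.11.3, 6.11.4.3 to 6.11.4.5 and 6.11.5.

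**Conclusion.** The covariate sets differ as described, without explanation, and aligning them is worthwhile at low priority. The expected benefit is a modest gain in precision at Week 28 whose size the documents do not allow one to state. The range of about -0.7% to -9% in the SE, with a possible loss of about 1%, rests on an assumed R² of 2 to 10% (0% for the loss), the SAP's SD of 5.3 and correlation of 0.5, compound symmetry, complete data and 100 patients. The slope component and the stated power above 99% are unaffected.

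A reader might infer that the primary analysis is biased or invalid. It is not: the current model is valid and adjusts for the stratification variable.

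**What to change.** Before unblinding:

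1. Add baseline MMSE-2 (continuous), age and gender as fixed effects to both MMRM code blocks in SAP 6.11.2 and to the text, with gender also in the CLASS statement.
2. Where the model is reused, avoid duplicate MMSE-2 terms. In 6.11.4.4 keep only the grouped MMSE-2 term. In 6.11.5.2, where MMSE-2 is the outcome, enter its baseline value once.
3. Record the change in SAP section 9. Protocol section 9 says that a modification of the primary analysis will also be reflected in a protocol amendment, so amend Protocol 9.4 accordingly.

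The cost is three degrees of freedom, a check of the sections that reuse the model, and the documentation. No new data are needed.

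### One baseline SIB coefficient for all visits can cost the Week 28 contrast some precision, and biases it only if baseline-related dropout also differs between arms

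*SAP*

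**What the plan says.** SAP 6.11.2 describes the primary MMRM as fitted "with SIB measured at baseline as covariate, visit treated as a continuous as well as categorical variable, treatment and treatment by visit interaction". The outcome is "the change from baseline in SIB total score at weeks 5, 9, 13, 15, 20, 24, 28, and 30", eight visits in all, with "the primary comparison being the difference in group means of SIB from baseline at Week 28". On covariance it says: "Correlation between repeated observations within a subject will be accounted for by specifying an unstructured correlation".

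The code agrees with the text. The primary statement is `model sibdiff = sibbase trt01pn avisitd trt01pn* avisitd`, quoted here as "model sibdiff = sibbase trt01pn avisitd trt01pn* avisitd", and the sensitivity statement is "model sibdiff = sibbase trt01pn avisitn trt01pn* avisitn". In both, treatment is crossed with visit and baseline SIB is not.

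The PP, CAS and best-case/worst-case analyses (6.11.3) reuse the primary model. The SIB analyses in 6.11.4.3 and 6.11.4.4 and the exploratory MMRMs in 6.11.5 also refer back to it. The single-visit ANCOVAs in 6.11.4.1 and 6.11.4.2 use "treatment group as factor, and baseline SIB total score, baseline MMSE-2 score, age and gender as covariates".

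On missing data, 6.11.2 says that an approach "such as MMRM will produce unbiased estimates of the treatment effect if the missingness is ignorable".

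**The concern.** A main-effect baseline term assumes that one SIB point at baseline predicts the same difference in change at Week 5 as at Week 30. The SAP gives no reason for this. Entry SIB runs from 60 to 93 on a 0-100 scale (Protocol 4.4.1 and 6.0.2.2), so a ceiling, or decline that depends on severity, could make the relation shift over seven months.

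Two things would follow from a shift. The unmodelled part goes into the residual variance at Week 28, so the standard error grows. Also, the SAP's statement about ignorable missingness needs a correct mean model, which 6.11.2 does not mention. Dropout that depends on baseline SIB is missing at random, yet a wrong baseline term can still leave bias. The categorical-visit model carries the same restriction, so it would not reveal the problem.

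**Working it through.** **1. The plan's own figure.** SAP section 4 gives σ = 5.3, ρ = 0.5, n = 8, s_x² = 127, d = 0.15 and two-sided α = 0.05. Solving Eq 1 for power: Φ(√[m·n·s_x²·d² / (2σ²(1−ρ))] − 1.96).

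- m = 50: √(50·8·127·0.0225 / 28.09) = √40.69 = 6.38, so power is 99.9995%.
- m = 40 (20% dropout): √32.55 = 5.71, so power is 99.99%.

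The stated figure above 99% reproduces. The listed weeks (0, 5, 9, 13, 15, 20, 24, 28) give a variance of 79.4 (divisor n), not 127, but power is then still 99.9% and 99.5%.

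**2. Mechanism.** Let β_t be the true baseline coefficient at visit t and β the single fitted one. The misfit for subject i is (β_t − β)(B_i − B̄).

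- Residual variance at visit t gains (β_t − β)²·Var(B). This is the precision loss.
- The arm contrast at visit t is disturbed roughly by (β_t − β) times the difference in mean baseline SIB between the arms among those still observed. Randomization makes that difference zero in expectation at entry. Dropout that depends on baseline in the same way in both arms keeps it at zero. Only an arm-specific relation moves it.

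**3. Simulation on the SAP's σ and ρ.** Effect 0.15 per week, which is 4.2 points at Week 28. Assumed, not in the documents: uniform baseline 60-93 (SD about 9.5), coefficient change from Week 5 to Week 28 of −0.1, −0.2 or −0.4, and the dropout pattern, with 18-19% lost before Week 28. Maximum likelihood, unstructured covariance. The with-dropout rows use 300,000 subjects (Monte Carlo SE 0.016-0.018); the complete-data row uses 20,000. SEs are scaled to 100 subjects. Each cell shows the planned model, then the model with baseline-by-time.

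| | −0.1 | −0.2 | −0.4 |
|---|---|---|---|
| SE, complete data | 0.848 / 0.844 (+0.5%) | 0.871 / 0.855 (+1.9%) | 0.912 / 0.853 (+6.9%) |
| SE, dropout alike in both arms | 0.904 / 0.898 (+0.7%) | 0.923 / 0.897 (+2.9%) | 1.003 / 0.896 (+11.9%) |
| Bias, dropout alike in both arms | −0.03 / −0.03 | −0.01 / −0.01 | +0.01 / +0.01 |
| Bias, baseline-related in active arm only | −0.14 / −0.01 | −0.29 / −0.03 | −0.44 / +0.02 |
| Bias, opposite relation in the two arms | −0.23 / −0.01 | −0.44 / −0.02 | −0.75 / +0.02 |

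The categorical-visit model behaves the same way. With opposite relations and a change of −0.4 (20,000 subjects), its bias is −0.78 as planned and 0.00 with the added term.

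With no change in the coefficient, 600 trials of 100 subjects gave empirical SDs of 0.903 v 0.903 (dropout alike) and 0.909 v 0.917 (opposite). The extra term therefore costs under 1%.

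**4. A change in the other direction.** No drug effect, 50 per arm. Assumed: baseline mean 78, SD 9, limited to 60-93; residual SD about 7.9 at Week 28; coefficient moving from −0.1 at Week 5 to +0.1, +0.2 or +0.3 at Week 28.

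- Complete-data SEs: 1.300 v 1.279 (+1.6%), 1.333 v 1.288 (+3.5%), 1.362 v 1.285 (+6.0%).
- Bias with 20% dropout per arm (bryostatin 35% below and 5% above the baseline mean, placebo unrelated to baseline): +0.24, +0.30, +0.34, against +0.04, +0.01, −0.03 with the added term (Monte Carlo SE about 0.035).

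**5. A further simulation** on σ = 5.3 and ρ = 0.5, with changes of 0.2-0.4, gave SE penalties of about 2-8% with complete data and 3-12% with about 20% dropout. Bias was about 0.15-0.6 points, and only when the baseline-dropout relation differed between arms.

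**6. Effect on power.** In the worst row of step 3, 4.2/1.00 − 1.96 = 2.24 gives 98.7%, against 4.2/0.90 − 1.96 = 2.71, which gives 99.7%.

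**The case against.** A main-effect baseline term is a permissible, fully pre-specified choice, and the documents give no evidence for either condition. This stands.

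- **Changing coefficient.** No value is given at any visit. A ceiling pushes the coefficient negative and faster decline in sicker patients pushes it positive, so even the sign is open. Regression to the mean enters late change scores as well as early ones, so it does not argue for a change.
- **Arm-specific dropout.** In NTRP101-203, completion was 87.3% on bryostatin and 85.7% on placebo, although the bryostatin arm was the more impaired at baseline (73.7 v 78.6; Protocol 2.1.1.2). In NTRP101-202, 76.9% of randomized subjects had a Week 13 SIB, and treatment-related TEAEs affected 37.0% on 20 µg against 16.7% on placebo (2.1.2.2, 2.1.2.3). That makes unequal dropout conceivable, but nothing links dropout to baseline SIB. Protocol 6.1.22 also encourages SIB visits after drug is stopped.
- **Stratification.** Randomization is stratified by baseline SIB, which limits imbalance at entry. It does not control who remains at Week 28, and it does not remove the misfit from the model's residual variance.
- **The ANCOVAs.** A one-visit model can only have one baseline coefficient for that visit, so 6.11.4.2 is not inconsistent with 6.11.2.

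The objection does not answer two facts: no planned analysis relaxes the restriction, and relaxing it costs almost nothing.

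**Conclusion.** The point holds as a modest, conditional weakness. The restriction is certain from the text and code. Its cost depends on an assumed change in the coefficient. For a change of 0.2-0.4 per SIB point, the standard error is about 2-8% larger with complete data and 3-12% larger with 20% dropout. If the coefficient is constant, nothing is lost.

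Bias requires both a changing coefficient and a baseline-dropout relation that differs between arms. It was then about 0.15-0.6 points (4-15% of the 4-point target), and 0.75 in the most extreme pattern tried. The direction is unknown: the scenarios in step 3 shrink the effect and those in step 4 inflate it.

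Three stronger readings are tempting but not supported:

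- **Baseline-related dropout by itself biases the contrast.** It does not: when the relation is alike in both arms, the planned and extended models give the same answer.
- **The model may manufacture a drug effect.** In step 4, bias/SE is 0.239/1.300 = 0.18 to 0.343/1.362 = 0.25. This raises two-sided type I error from 5% to only about 5.4-5.7%, under a dropout pattern that nothing in the documents suggests.
- **The power claim fails.** On the SAP's own σ and ρ, the worst precision loss moves power from 99.7% to 98.7%.

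**What to change.** Before unblinding:

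- Add `sibbase*avisitd` to the primary MODEL statement and `sibbase*avisitn` to the categorical sensitivity MODEL statement in 6.11.2. Both Week 28 ESTIMATE statements stay as they are.
- Use the same term in the SIB MMRMs of 6.11.4.3 and 6.11.4.4, and the matching baseline-by-visit term for each scale in the exploratory MMRMs of 6.11.5. The 6.11.3 analyses follow the primary model.
- Handle 6.11.4.5 separately. Its slope code has no `sibbase` term, so the change cannot simply be copied there.
- State in 6.11.2 that the claim of no bias under ignorable missingness also needs a correctly specified mean model.

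The cost is 1 parameter in the primary model and 7 in the sensitivity model (eight visits less one), no new data, and under about 1% in standard error if the coefficient is constant. The timing matters, because the same term added after unblinding could look data-driven.
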